5.4.3.8 Management and Dose Modification Guidelines for Hypertension

For patient experiencing an increase in systolic and/or diastolic blood pressure that is persistent and may be associated with the study treatment, recommendations for the clinical management of hypertension are described in Table 12.

Table 12: Management and Dose Modification Guidelines for Hypertension

Hypertension	Action and Dose Modification

(Scenario A)
 
Asymptomatic and persistent^a SBP of ≥ 140 and < 160 mmHg, or DBP ≥ 90 and < 100 mmHg, or
 
Clinically significant increase in DBP of 20 mmHg (but DBP still <100 mmHg).
	
Continue dabrafenib and trametinib and HCQ/placebo at the current dose
 
Adjust current or initiate new antihypertensive medication
 
Titrate antihypertensive medication(s) during the next 2 weeks as indicated to achieve well-controlled^b BP
 
If BP is not well controlled within 2 weeks, consider referral to a specialist and go to scenario (B).

(Scenario B)
 
Asymptomatic SBP ≥ 160 mmHg, or DBP ≥100 mmHg, or
	
Interrupt dabrafenib and trametinib if clinically indicated but continue HCQ/placebo
 
Adjust current or initiate new antihypertensive medication(s)

Hypertension	Action and Dose Modification
Failure to achieve well-controlled BP within 2 weeks in Scenario A	
Titrate antihypertensive medication(s) during the next 2 weeks to achieve well-controlled BP
 
Once BP is well controlled^b, restart dabrafenib and trametinib reduced by one dose level^c and continue HCQ/placebo

(Scenario C) Symptomatic ^d hypertension or Persistent SBP \geq 160 mmHg, or DBP \geq 100 mmHg, despite antihypertensive medication and dose reduction of study treatment	
Interrupt dabrafenib, trametinib and HCQ/placebo treatment
 
Adjust current or initiate new antihypertensive medication(s)
 
Titrate antihypertensive medication during the next 2 weeks to achieve well-controlled BP
 
Referral to a specialist for further evaluation and follow-up is recommended
 
Once BP is well controlled, restart 3 study treatments reduced by one dose level^c

(Scenario D) Refractory hypertension unresponsive to above interventions, or having hypertensive crisis.	
Permanently discontinue study treatment
 
Continue follow-up per protocol.

- a. Hypertension detected in two separate readings during up to three consecutive visits
- b. Well-controlled blood pressure defined as SBP \leq 140 mm Hg and DBP \leq 90 mm Hg in two separate readings during up to three consecutive visits.
- c. Escalation of study treatment to previous dose level can be considered if BPs remain well-controlled for 4 weeks after restarting of study treatment.

Symptomatic hypertension defined as hypertension aggravated by symptoms (e.g., headache, light-headedness, vertigo, tinnitus, episodes of fainting) that resolve after the blood pressure is controlled within the normal range.

5.4.3.9 Other dabrafenib-specific adverse events and recommended management

Palmar plantar erythrodysesthesia (PPES) – Measures for PPES should include:

Lifestyle modification: avoidance of hot water, traumatic activity, constrictive footwear, or excessive friction on the skin and the use of thick cotton socks and gloves, and shoes with padded insoles

- Symptomatic treatments: apply moisturizing creams frequently, topical keratolytics (e.g. urea 20-40% cream, salicylic acid 6%, tazarotene 0.1% cream, fluorouracil 5% cream), clobetasol propionate 0.05% ointment for erythematous areas, topical lidocaine 2%, and / or systemic pain medication such as nonsteroidal anti-inflammatory drugs, codeine, and pregabalin for pain.
- Dose modification may also be required.

Pancreatitis – In the event of abdominal pain or suspected pancreatitis, amylase and lipase laboratory samples should be collected for confirmation of the

diagnosis. Patients should be closely monitored when restarting dabrafenib after an episode of pancreatitis.

Uveitis: Treatment with dabrafenib has been associated with the development of uveitis, including iritis. Monitor patients for visual signs and symptoms (such as, change in vision, photophobia and eye pain) during therapy.

Hyperglycemia: Hyperglycemia requiring an increase in the dose of, or initiation of insulin or oral therapy can occur with dabrafenib. Monitor serum glucose levels as clinically appropriate during treatment with dabrafenib in patient with pre-existing diabetes or hyperglycemia. Advise patients to report symptoms of severe hyperglycemia such as excessive thirst or any increase in the volume or frequency of urination.

Investigators should always err on the side of caution in these settings if treatment-related toxicity is a possibility.

5.4.3.10 Ocular Toxicity

Due to the known ocular toxicities associated with BRAF and MEK inhibitors and the potential for toxicity with HCQ, an ophthalmic exam at baseline and yearly thereafter is required. The standard of care for patients on HCQ is that the ophthalmologist performs visual field 10-2 test, plus one of the three other highly sensitive screening tests: the FAF (fundus autofluorescence imaging), the SD-OCT (spectral domain optical coherence), or the multifocal electroretinogram (mfERG). Episodes of visual changes have been observed in patients receiving trametinib, dabrafenib, and combination therapy. An ophthalmologist should be consulted if changes in vision develop.

However, if the visual changes are clearly unrelated to study treatment (e.g., allergic conjunctivitis), then monitor closely as it may be reasonable to defer ophthalmic examination. Treatment with dabrafenib has been associated with the development of uveitis, including iritis. Monitor patients for visual signs and symptoms (such as, change in vision, photophobia and eye pain) during therapy. Special attention should be given to retinal findings (e.g., retinal pigment epithelial detachment (RPED) or retinovascular abnormalities (i.e., branch or central retinal vein occlusions (RVO)).

With particular regard to visual field deficits patients should be cautioned to report any visual symptoms, particularly difficulty seeing entire words or faces, intolerance to glare, decreased night vision, or loss of peripheral vision. **These symptoms of retinal toxicity or subclinical evidence of retinal toxicity on eye exams should prompt drug discontinuation and ophthalmologic evaluation.**

Patients who discontinue HCQ/placebo permanently may

stay on dabrafenib and/or trametinib at the discretion of the treating physician in consultation with an ophthalmologist.

Guidelines regarding management and dose reduction for visual changes and/or ophthalmic examination findings considered to be related to study treatment are provided in Tables 13, 14, and 15.

Table 13: Management and Dose Modification Guidelines for Visual Changes and/or Ophthalmic Examination Findings

CTCAE Grade ^a	Adverse Event Management	Action and Dose Modification
Grade 1 ^b	
 Consult ophthalmologist within 7 days of onset 	
 If dilated fundus examination cannot be performed within 7 days of onset, interrupt trametinib and hydroxychloroquine until RPED, RVO, and visual field deficit can be excluded by retina specialist/ophthalmologist. Dabrafenib may be continued. If RPED and RVO excluded, continue (or restart) trametinib and HCQ/placebo at same dose level If RPED suspected or diagnosed: see RPED dose modification table 14 below; report as SAE if diagnosed. If RVO diagnosed: Permanently discontinue trametinib and report as SAE.
Grade 2 and Grade 3	
 Consult ophthalmologist immediately Interrupt trametinib and HCQ/placebo. Dabrafenib may be continued. 	
 If RPED and RVO excluded, restart trametinib and HCQ at same dose level. If RPED diagnosed, see RPED dose modification table below; report as SAE. If RVO diagnosed: Permanently discontinue trametinib and report as SAE
Grade 4	
 Consult ophthalmologist immediately Interrupt trametinib and HCQ/placebo. Dabrafenib may be continued. 	
 If RPED and RVO excluded, may consider restarting trametinib at same or reduced dose If RVO or RPED diagnosed, permanently discontinue trametinib and report as SAE.

Abbreviations: RPED = retinal pigment epithelial detachment; CTCAE = Common Terminology Criteria for Adverse Events; RVO= retinal vein occlusion; SAE = serious adverse event

a Refers to the CTCAE 'Eye disorders – Other, specify'

b If visual changes are clearly unrelated to study treatment (e.g., allergic conjunctivitis), monitor closely but ophthalmic examination is not required.

Table 14: Recommended dose modifications for trametinib for retinal pigment epithelial detachments (RPED)

CTCAE Grade	Action and Dose Modification
Grade 1 RPED (Asymptomatic; clinical or diagnostic observations only)	
 Continue treatment with retinal evaluation each cycle (monthly) until resolution. If RPED worsens follow instructions below
Grade 2-3 RPED (Symptomatic with mild to moderate decrease in visual acuity; limiting instrumental ADL)	
 Interrupt trametinib and hydroxychloroquine/placebo Retinal evaluation each cycle (monthly) If improved to ≤ Grade 1, restart trametinib at lower dose (reduced by 0.5 mg) or discontinue in patients taking trametinib 1 mg daily

Table 15: Management of Ocular Toxicities

Ocular Toxicity	Action
Uveitis, conjunctivitis	
 Continue all therapies as long as effective local therapies can control inflammation
Retinal Vein occlusion, retinal pigment epithelial detachment (RPED), papilledema	
 See table 13 and 14
Visual field deficits	
 Discontinue HCQ/placebo

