5.4.2 General Guidelines for Toxicities and Dose Modifications

Guidelines for specific toxicities are outlined below, but general guidelines for toxicities not listed are provided in Table 5.

Table 4: General Dose modification guidelines for dabrafenib and trametinib for toxicities attributable to only dabrafenib and/or trametinib. These are general guidelines but for specific toxicities dose modification instructions may be different and are provided in the subsequent sections.

CTCAE Grade	Action and Dose Modification
Grade 1	
 Continue dabrafenib, trametinib and HCQ/placebo at current dose level Monitor closely

CTCAE Grade	Action and Dose Modification
	
 Provide supportive care according to institutional standards
Grade 2	
 Interrupt dabrafenib and trametinib if clinically indicated, continue HCQ/placebo Monitor closely Provide supportive care according to institutional standards When toxicity resolves to Grade 1 or baseline, restart dabrafenib and trametinib treatment at current dose level
Grade 3	
 Interrupt dabrafenib and trametinib if clinically indicated, continue HCQ/placebo Monitor closely Provide supportive care according to institutional standards When toxicity resolves to Grade 1 or baseline, restart dabrafenib and trametinib both reduced by one dose level If the Grade 3 toxicity recurs, interrupt study treatment When toxicity resolves to Grade 1 or baseline, restart dabrafenib and trametinib both reduced by another dose level
Grade 4	
 Interrupt dabrafenib and trametinib, continue HCQ/placebo Monitor closely Provide supportive care according to institutional standards If event resolves to Grade 1 or baseline patient may continue dabrafenib and trametinib both reduced by one dose level If event does not resolve permanently discontinue study treatment

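### Table 15 sends papilledema to Tables 13 and 14, neither of which names it, and Table 13 lets trametinib restart at Grades 2-4 without any improvement

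*Combined protocol and SAP*

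**What the plan says.** Section 5.4.3.10 gives its ocular dose rules in Tables 13 to 15, for findings considered related to study treatment. In Table 15 one row reads "Retinal Vein occlusion, retinal pigment epithelial detachment (RPED), papilledema", and its action column only points to Tables 13 and 14.

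- **Table 13** covers visual changes and eye-examination findings. At Grades 2-4 it calls for immediate ophthalmology consultation and says: "Interrupt trametinib and HCQ/placebo. Dabrafenib may be continued". For Grades 2-3 it continues: "If RPED and RVO excluded, restart trametinib and HCQ at same dose level". For Grade 4: "If RPED and RVO excluded, may consider restarting trametinib at same or reduced dose". Its footnote a says of the grade column: "Refers to the CTCAE 'Eye disorders – Other, specify".
- **Table 14** is for RPED only. Grade 1: "Continue treatment with retinal evaluation each cycle (monthly) until resolution". Grades 2-3: interrupt trametinib and HCQ/placebo and, after improvement to Grade 1 or lower, "restart trametinib at lower dose (reduced by 0.5 mg", or stop trametinib in patients already at 1 mg daily.
- **Table 4** (Section 5.4.2) is the general rule for toxicities attributed only to dabrafenib and/or trametinib. At Grades 2-3: "Interrupt dabrafenib and trametinib if clinically indicated, continue HCQ/placebo". Restart waits for Grade 1 or baseline, at the current dose after Grade 2 and one level lower after Grades 3-4. Study treatment stops permanently if a Grade 4 event does not resolve.
- **Section 5.4.1.2** holds HCQ/placebo for any adverse event of Grade 3 or higher until Grade 1 or lower, then allows restart at a reduced dose.

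**The concern.** Papilledema is in the rare-but-serious column of the trametinib risk list (Section 5.3.2). The protocol recognises it in Table 15 but sends the site to two tables that never mention it. The only rows a site can apply are those of Table 13, where the restart depends on excluding two other diagnoses and not on the course of the papilledema. A patient whose papilledema is neither RPED nor RVO meets that condition at once. At Grades 2-3 the text then tells the site to restart trametinib at full dose, even if the finding is unchanged. At stake is a patient being put back on the suspect drug during an unresolved serious eye event.

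**Working it through.** The point concerns the text, so the check sets the three tables side by side.

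| | Table 13, RPED and RVO excluded | Table 4, general | Table 14, RPED only |
|---|---|---|---|
| Grade 1 | Continue; interrupt trametinib and HCQ if no fundus examination within 7 days | Continue | Continue, monthly retinal evaluation |
| Grade 2, onset | Interrupt trametinib and HCQ/placebo; ophthalmologist at once | Interrupt dabrafenib and trametinib if clinically indicated | Interrupt trametinib and HCQ/placebo |
| Grade 2, trametinib restart | No improvement needed; same dose | Grade 1 or baseline; current dose | Grade 1 or lower; 0.5 mg lower |
| Grade 3, onset | As Grade 2 | As Grade 2 | As Grade 2 |
| Grade 3, trametinib restart | No improvement needed; same dose | Grade 1 or baseline; one level lower | Grade 1 or lower; 0.5 mg lower |
| Grade 4, onset | As Grade 2 | Interrupt dabrafenib and trametinib | No row |
| Grade 4, trametinib restart | Optional; no improvement needed; same or reduced dose | Grade 1 or baseline; one level lower; stop if unresolved | No row |

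1. **Grade 1.** All three tables allow continuation, so there is no defect at this grade.
2. **Onset, Grades 2-3.** Table 13 is stricter than Table 4: it requires interruption, where Table 4 leaves this to clinical judgement.
3. **Restart, Grades 2-4.** Table 13 is the only one of the three without an improvement condition. At Grade 3 it is also looser than Table 4 on dose. At Grade 4 it permits the same dose but does not require it.
4. **Which rule governs.** Section 5.4.2 says that instructions for specific toxicities may differ from the general table. Where Table 13 applies, a site may therefore take it to displace Table 4's resolution condition.
5. **Footnote a.** The trametinib risk list enters RVO and RPED under the heading for other eye disorders, but papilledema as a term of its own. Read strictly, the footnote would place papilledema outside Table 13. No papilledema-specific rule would then remain, only general ones: Table 4, the Section 5.4.1.2 hold on HCQ/placebo, and ophthalmology consultation for changes in vision. That fallback is untidy. Section 5.4.2 points to Table 5, which is the pyrexia table, for toxicities not listed, and papilledema is listed in Table 15.
6. **HCQ/placebo, separate and not specific to papilledema.** For a Grade 3 finding with RPED and RVO excluded, Table 13 restarts HCQ at the same dose. Section 5.4.1.2 requires Grade 1 or lower first and then allows a reduced dose. Table 4 conflicts with the same section more directly, because it continues HCQ/placebo at Grades 3 and 4.
7. **Size.** The risk-list column is below 3%, from 1111 trametinib patients, at any grade. Both arms receive trametinib and 84 patients are planned: 0.03 x 84 = 2.52. If that limit carries over, the expected number with papilledema of any grade is below 2.52. The affected patients (treatment-related, Grades 2-4, RPED and RVO excluded) are a subset for which the documents give no rate.

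**The case against.** The strongest defence is that the cross-reference works. Table 13's title is broad enough for papilledema, Table 15 sends it there expressly, and the response at onset is firm: trametinib and HCQ/placebo are interrupted and an ophthalmologist sees the patient immediately. At Grade 4 the restart is discretionary, and Section 5.7 ends therapy for unacceptable toxicity. All of this stands, but it concerns onset and discretion. The Grade 2-3 row states a restart without making it depend on improvement or on the ophthalmologist's agreement. Nothing in Table 13 suggests that a looser rule for papilledema was intended.

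Three stronger readings are tempting, and the documents do not support them.

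- *A reader might infer that, under footnote a, sites have no instruction at all.* The general rules in step 5 would still apply, and Table 4 supplies the missing resolution condition. The strict reading is itself strained, since the footnote says which term the grades refer to and Table 15 routes papilledema to the table by name.
- *A reader might infer that dabrafenib is left contradictory*, because Section 5.4.1.1 lists RVO and RPED, but not papilledema, among the trametinib-only exceptions. If Table 13 applies, it says that dabrafenib may be continued, and Section 5.4.2 allows specific instructions to differ from general ones.
- *A reader might put a probability on the problem.* Assumed subset rates of 0.1%, 0.5% and 1% in 1 - (1 - r)^84 give 8%, 34% and 57% for at least one case. None of these rates comes from the documents. The formula also counts occurrence, not a restart during unresolved papilledema.

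**Conclusion.** Wrong as written, minor. If Table 13 is followed as Table 15 directs, Grade 2-3 papilledema with RPED and RVO excluded leads to a same-dose trametinib restart whether or not it has improved. Grade 4 papilledema may lead to a restart on the same terms. The protocol's own standards in Tables 4 and 14 require improvement first. The conclusion rests on reading Table 13 as covering papilledema, which is the natural reading. On the strict reading of footnote a, the defect is instead a missing papilledema-specific rule, with general rules behind it.

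The size is small. The only figure is the any-grade column limit of below 3%, and the frequency in the affected subset is unknown. No effect on the primary endpoint is claimed. The HCQ/placebo conflict at Grade 3 in Table 13, and at Grades 3-4 in Table 4, is a separate inconsistency that holds whichever way footnote a is read.

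**What to change.** Give papilledema its own row in Table 15, or a branch in Table 13:

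- Grades 2-4: interrupt trametinib and HCQ/placebo, keeping the immediate ophthalmology consultation.
- Do not restart trametinib until resolution to Grade 1 or baseline, and restart one dose level lower after Grade 3 or higher.
- Discontinue permanently if Grade 4 does not resolve, as in Table 4. Mandatory discontinuation for non-resolution at Grades 2-3 would go beyond both Table 4 and Table 14, so it is not proposed here.

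The row should also say when HCQ/placebo resumes after a Grade 2 event; from Grade 3 upward Section 5.4.1.2 already answers this. The final clinical content is for the sponsor's clinical team.

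Separately, change Table 13's Grade 3 restart of HCQ/placebo to match Section 5.4.1.2 (hold to Grade 1 or lower, then a reduced dose), and reconcile Table 4's continuation of HCQ/placebo at Grades 3-4 with the same rule.

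The cost is one added row and a few changed lines in the next amendment, with slightly more drug interruption in very few patients. No new tests, visits or patients are needed.

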5.4.3.11 Cutaneous Squamous Cell Carcinoma (cuSCC)
 Cases of cuSCC (which include those classified as keratoacanthoma or mixed keratoacanthoma subtype) have been observed in patient treated with dabrafenib. Approximately 70% of events occurred within the first 12 weeks of treatment with a median time to onset of 8 weeks. Dose modification or interruption of study treatment is not required for cuSCC or KA, however cuSCC should be reported as an SAE if it meets the reporting requirements outline in Section [5.2.10](#).

The cuSCC risk management plan includes (at a minimum) regular, thorough skin examinations by a dermatologist or melanoma oncology specialist trained to diagnose and treat these lesions, regular head and neck exams by the treating physician. In patients who develop cuSCC or any suspicious skin lesions during the trial, definitive treatment (i.e., surgical excision) of any SCC/KA or other suspicious lesion(s) is required (shave biopsies are not recommended), and the excised tissue is to be sent to a pathology laboratory. A complete dermatological history of prior medications and cuSCC risk factors (i.e., radiation therapy, sun exposure, immunosuppression, prior SCC, use of tanning beds, precursor lesions and photochemotherapy for psoriasis) must be collected.

- A designated dermatologist or the treating medical oncologist, if he/she is adept at skin exams will be available to perform skin exams to monitor for cuSCC,

BCC, actinic keratosis, keratoacanthoma and second primary melanomas. Any lesion suspected of being a SCC, BCC, actinic keratosis, keratoacanthoma or second primary melanoma should be appropriately mapped, photographed, with the photos stored digitally and made available upon request.

- Any suspicious lesions identified at baseline and while on D+T+ placebo or D+T+HCQ must be fully excised and sent for pathological examination (shave biopsies are not recommended).
- Actinic keratosis, keratoacanthoma or other skin conditions should be treated as per local standard of care.

5.4.3.12 New primary melanoma

New primary melanomas have been reported in patients treated with dabrafenib. These were identified within the first 5 months of therapy and did not require treatment modification other than excision. Monitoring for skin lesions should occur as described for cuSCC.

5.5 Drug interactions:

Table 16: Prohibited medications with CYP3A or CYP2C* Interactions

PROHIBITED – Strong inducers of CYP3A or CYP2C8, since concentrations of dabrafenib may be decreased	
Class	Drugs
Antibiotics	Rifamycin class agents (e.g., rifampin, rifabutin, rifapentine),
Anticonvulsant	Carbamazepine, oxcarbazepine, phenobarbital, phenytoin, s-mephentyoin
Miscellaneous	bosentan, St-John's wort

PROHIBITED – Strong inhibitors of CYP3A, or CYP2C8 since concentrations of dabrafenib may be increased	
Class/Therapeutic Area	Drugs/Agents
Antibiotics	Clarithromycin, telithromycin, troleandomycin
Antidepressant	Nefazodone
Antifungals	Itraconazole, ketoconazole, posaconazole, voriconazole
Hyperlipidemia	Gemfibrozil
Antiretroviral	ritonavir, saquinavir, atazanavir
Miscellaneous	Conivaptan

Table 17: USE WITH CAUTION: Moderate inhibitors of CYP3A, or CYP2C8 since concentrations of dabrafenib may be increased

Class/Therapeutic Area	Moderate CYP3A and CYP2C8 Inhibitors
Antiarrhythmics	Diltiazem, verapamil
Antibiotic	Erythromycin

Class/Therapeutic Area	Moderate CYP3A and CYP2C8 Inhibitors
Antifungal	Fluconazole
Miscellaneous	Aprepitant
USE WITH CAUTION: Co-administration of these drugs with study treatment may result in loss of efficacy. Monitor patient for loss of efficacy or substitute with another medication.	
Class/Therapeutic Area	CYP3A4, CYP2B6, CYP2C8, CYP2C9, CYP2C19 or Transporter Substrates that May be Affected by Induction
Analgesics	Alfentanil, buprenorphine, celecoxib, codeine, fentanyl, methadone, oxycodone
Antiarrhythmics	Disopyramide, dronedarone, mexiletine, propafenone, quinidine
Antibiotics	Chloramphenicol, doxycycline, erythromycin, moxifloxacin
Anticoagulants/ Antiplatelets	Cilostazole, warfarin
Anticonvulsants	Divalproex, lamotrigine, valproate, zonisamide
Antidepressants and Antipsychotics	Aripiprazole, bupropion, buspirone, desipramine, haloperidol, mirtazapine, pimozide, quetiapine, trazodone, amitriptyline, clomipramine, imipramine
Antidiabetics	Glyburide, saxagliptin, tolbutamide, nateglinide, pioglitazone, repaglinide, rosiglitazone
Antifungals	Caspofungin, fluconazole, terbinafine
Antihistamines	Astemizole, chlorpheniramine, ebastine
Antihypertensives	Amlodipine, diltiazem, felodipine, nifedipine, nilvadipine, nisoldipine, verapamil
Antimigraine Agents	Diergotamine, eletriptan, ergotamine
Corticosteroids	Dexamethasone, methylprednisolone, oral budesonide
Erectile Dysfunction Agents	Sildenafil, tadalafil, vardenafil
HMG-CoA Reductase Inhibitors	Atorvastatin, lovastatin, simvastatin, rosuvastatin, pravastatin
Hypnotics and Sedatives	Alprazolam, brotizolam, diazepam, estazolam, midazolam, triazolam, zolpidem, zopiclone
Immunosuppressants	Everolimus, sirolimus, tacrolimus
Miscellaneous	Aprepitant, cisapride, darifenacin, digoxin, disopyramide, leflunomide, methohexitol, oral contraceptives, quinine, ranitidine, solifenacin, sulfasalazine, tramadol, tolvaptan, chloroquine, zopiclone
Selective Aldosterone Blockers	Eplerenone
USE WITH CAUTION: Co-administration of drugs that increase gastric pH should be used with caution when administered with dabrafenib as exposure to dabrafenib may be decreased	
pH altering agents	dexlansoprazole, esomeprazole, famotidine, ilaprazole, lansoprazole, omeprazole, pantoprazole, rabeprazole, ranitidine

